2.3.1 Patient disposition

The following listings will be presented:

- Subjects who discontinued prior to Epoch 2 on Safety Set
- Study completion during Epoch 2 on Safety Set

2.4 Treatments (study treatment, rescue medication, concomitant therapies, compliance)

2.4.1 Study treatment / compliance

Exposure to study treatment will be listed. Also, the number of doses will be listed for individual patients.

For each patient, duration of exposure will be defined as (date of last visit in study) – (date of first administration of extension treatment) + 1.

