5.5.4 Instructions for prescribing and taking study treatment

The s.c. injections of investigational treatment may be administered into the patient's arm or thigh. Detailed instructions on the preparation and administration of the study drugs will be described in the Pharmacist Manual provided in the CACZ885N2301 study.

All patients will receive 1 or 2 s.c. injections every 4 or 8 weeks based on the final dose regimen received in the CACZ885N2301 study and depending upon criteria met for up-titration ([Section 3.1.2](#)) until TD/ PSW.

All dosages prescribed and dispensed to the patient and all dose changes during the study must be recorded on the Dosage Administration Record CRF.

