5.5.8 Prohibited medication

Use of the treatments displayed in [Table 5-1](#) is NOT allowed after Screening. Once canakinumab is approved for Periodic Fever Syndromes (TRAPS, HIDS/MKD, or crFMF), it can be used according to the package insert.

Table 5-1 Prohibited treatment

Medication	Action to be taken
Anakinra	Investigational treatment to be discontinued ²
Riloncept, tocilizumab, rituximab and any other biologics ¹ (investigational or marketed)	Investigational treatment to be discontinued ²
Etanercept, adalimumab, infliximab, or any TNF inhibitor (investigational or marketed)	Investigational treatment to be discontinued ²
Leflunomide, thalidomide, cyclosporine, or i.v. Ig	Investigational treatment to be discontinued ²
Tofacitinib	Investigational treatment to be discontinued ²
6-Merceptopurine, azathioprine, cyclophosphamide, or chlorambucil	Investigational treatment to be discontinued ²
Any other investigational non-biological drug	Investigational treatment to be discontinued ²
Any live vaccination ¹	Investigational treatment to be discontinued ²
Treatment for tuberculosis	Investigational treatment to be discontinued

¹ It is recommended not to initiate any live vaccination or biologic treatment until 3 months after the last dose of investigational treatment. Killed or inactivated vaccines may be permitted according to the investigator's discretion.

² Investigational treatments must be permanently discontinued but patient will remain in the study and will be followed-up for safety.

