5.6.2 Discontinuation of study treatment

Discontinuation of study treatment for a patient occurs when study drug is stopped earlier than the protocol planned duration, and can be initiated by either the patient or the investigator.

The investigator must discontinue study treatment for a given patient if, on balance, he/she believes that continuation would negatively impact the risk/benefit of trial participation.

Study treatment must be discontinued under the following circumstances:

- Emergence of the following adverse events:
 - a. Absolute QTcF > 500 msec, confirmed by repeat electrocardiogram (ECG) measurements
 - b. Serious infections combined with neutropenia Common Toxicity Criteria (CTC) grades ≥ 1 (ANC < $2.0 \times 10^9/L$)
 - c. CKD as per NKF stages ≥ 4 : eGFR ≤ 29 mL/min/1.73 m²
 - d. Confirmed diagnosis of latent or active Tuberculosis
 - e. Onset of any malignancy
- Any of the following laboratory abnormalities:
 - a. Neutropenia CTC Grades ≥ 2 : ANC < $1.5 \times 10^9/L$
 - b. Thrombocytopenia CTC Grade 4: Platelets < $10.0 \times 10^9/L$
- Pregnancy
- Use of prohibited treatment as per [Table 5-1](#)
- Any other protocol deviation that results in a significant risk to the patient's safety

If discontinuation of study treatment occurs, the patient should NOT be considered withdrawn from the study. The patient should return to the clinic as soon as possible, after discontinuation of study drug, for a study treatment discontinuation visit. Treatment discontinuation visit assessments detailed in the "treatment discontinuation visit" in [Table 6-1](#) should be completed and recorded in the eCRF. The investigator must determine the primary reason for the patient's premature discontinuation of study treatment and record this information on the Dosage Administration eCRF.

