S = assessment to be recorded on source documentation only

*These assessments are also to be conducted for patients who discontinue

Visit 1 of this extension study and Visit 399 of the CACZ885N2301 study are conducted on the same day. Visit 1 and Visit 101 can be on the same day

1. Patients receiving ACZ885 q4w or up-titrated to q4w administration will come back every 4 weeks for unscheduled visits at Day 813, Day 869 and so forth in addition to the scheduled visits

2. These assessments are source documentation only and will not be entered into the CRF, because they will be used only for dose adjustment or judgement of up-titration due to flare. Flare is defined as simultaneous occurrence of a clinical flare and a serological flare defined as follows:

- PGA \geq 2 (clinical flare)

- CRP \geq 30 mg/L (serological flare)

3. Body weight to the nearest 0.1 kilogram (kg) in indoor clothing, but without shoes

4. The PGA (physician's global assessment) will be based on a 5-point scale:

- 0 = None (no) disease associated clinical signs and symptoms

- 1 = Minimal disease associated signs and symptoms

- 2 = Mild disease associated signs and symptoms

- 3 = Moderate disease associated signs and symptoms

- 4 = Severe disease associated signs and symptoms

5. CRP will be measured at the local laboratory, including any unscheduled visits. CRP value will be standardized to a normal range of 0-10 mg/L.

6. After canakinumab is approved for Periodic Fever Syndromes (TRAPS, HIDS, or crFMF) in Japan, all subjects who continue study treatment at the timing will be expected to perform V199 evaluation approximately 8 weeks after their most recent assessment visit, and then will enter the safety follow-up period.

7. If V 101 of this extension study and V 399 of the CACZ885N2301 study are conducted on the same day, Physical exam, PGA, CRP, weight, local tolerability will be assessed only one time.

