6.5 Safety

The safety assessments presented in this Section 6.5 are mandatory for all patients including those for whom study treatment must be permanently discontinued as detailed in [Section 5.6.2](#).

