9.3 Treatments

The exposure to investigational treatment (number of doses) and duration of exposure (days) during this study will be listed for the Safety Set.

Rescue medication will be also listed.

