2.1.1 General definitions

Table 2-1 General definitions

Terms	Definiton
Study treatment	The treatment by dosing the investigational drug, canakinumab.
Date of first administration of extension treatment	The first visit date that the study treatment is given for this extension study .
Date of last administration of study treatment	The last visit date that the study treatment is given.
Extension Day 1	Date of first administration of extension treatment
Extension Study Day	Extension Study Day is defined as (Event start date) – (Extension Day 1) + 1 for any event dated on or after Extension Day 1, or (Event start date) – (Extension Day 1) for any event dated before Extension Day 1.
Baseline	The last assessments obtained before the first dose of study treatment. This definition will be applied to percent change for creatinine clearance.

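### SAP 2.4.1 lists time in study under the label duration of exposure; if a patient stops drug and attends later visits, off-drug days count as exposure

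*SAP*

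**What the plan says.** Protocol 9.3 asks that exposure to investigational treatment be shown as number of doses and that "duration of exposure (days) during this study will be listed for the Safety Set". It does not define the duration. SAP 2.4.1 supplies the definition: "duration of exposure will be defined as (date of last visit in study) – (date of first administration of extension treatment) + 1". SAP Table 2-1 separately defines the date of last administration of study treatment ("The last visit date that the study treatment is given"), which the formula does not use. SAP section 4 records no change to the protocol-specified analyses.

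The protocol keeps stopping drug separate from leaving the study. Section 5.6.2: "If discontinuation of study treatment occurs, the patient should NOT be considered withdrawn from the study". Table 5-1, footnote 2, on prohibited medication: "Investigational treatments must be permanently discontinued but patient will remain in the study and will be followed-up for safety". Section 6.5 makes the safety assessments "mandatory for all patients including those for whom study treatment must be permanently discontinued". The asterisk note under Table 6-1 adds: "These assessments are also to be conducted for patients who discontinue".

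**The concern.** A quantity called duration of exposure should end at, or a stated time after, the last dose. This one ends at the last visit. The two agree while drug continues to the end, but they can part for a patient who stops drug and stays in the study, which the protocol provides for. Nothing in the formula then limits how much off-drug time is counted.

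What is at stake is how individual values are read. Adverse events are the primary variable, and individual listings are the only output. A reader who sets the date of an early stopper's event against the listed duration could take an off-drug event as on-drug. The dose count listed alongside helps, but it does not give the date of the last dose, particularly since a regimen may change from every 8 weeks (q8w) to every 4 weeks (q4w) during the study.

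**Working it through.** The plan states no exposure figure to reproduce, so I applied the formula to the visit days in protocol Table 6-1.

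**Visit days.** Core-study day = (week − 1) × 7 + 1. Weeks 113, 121 and 129 give Days 785, 841 and 897, as in the table. With the first extension dose assumed at Visit 101 (Day 785), Extension Day = core day − 785 + 1, so Visit 102 (Day 841) is Extension Day 57 and Visit 103 (Day 897) is Extension Day 113.

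**Comparator.** Neither document defines a post-dose window. I used last dose + window − 1, capped at the last visit recorded in the clinical database, with a 56-day window for everyone or a 28-day window for q4w. Duration to the last dose alone is shown as the lower bound.

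**Patient dosed to schedule.** Assume Visit 199 at Extension Day 337, with no dose at that visit. The SAP lists 337 days.
- q8w, last dose Day 281: min(281 + 56 − 1, 337) = 336, excess 1.
- q4w, last dose Day 309, 28-day window: min(309 + 28 − 1, 337) = 336, excess 1.
- q4w, last dose Day 309, 56-day window: min(309 + 56 − 1, 337) = 337, excess 0.

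**Early stopper.** Assume the last dose at Extension Day 57 and the last database visit w weeks later, at Extension Day 57 + 7w. The SAP lists 57 + 7w days. The comparator is min(57 + 56 − 1, 57 + 7w) = min(112, 57 + 7w), or min(57 + 28 − 1, 57 + 7w) = min(84, 57 + 7w).

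| Last visit after last dose | SAP lists | To last dose | 56-day window (excess) | 28-day window (excess) |
|---|---|---|---|---|
| 4 weeks | 85 | 57 | 85 (0) | 84 (1) |
| 8 weeks | 113 | 57 | 112 (1) | 84 (29) |
| 24 weeks | 225 | 57 | 112 (113) | 84 (141) |
| 48 weeks | 393 | 57 | 112 (281) | 84 (309) |

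Once the window has passed, each further 8-week visit attended adds 56 days.

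**Which rows the schedule supports.** Section 5.6.2 asks for the discontinuation visit as soon as possible after stopping. Table 6-1 puts Visit 199, discontinuation and withdrawal in one column, followed only by the safety follow-up. The asterisked rows are exactly those filled in that column, plus the follow-up contact; weight, PGA, CRP and dosing are blank there and carry no asterisk. The asterisk note is therefore fully explained by the discontinuation visit and the follow-up contact. The 4-week row, or a shorter gap, fits this path. The 24- and 48-week rows need visits that the documents neither schedule nor exclude.

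**The follow-up contact.** Sections 3.1.2 and 5.6.1 call it a visit, possibly by telephone, and Table 6-1 records it in source documents only. If it were counted as the last visit, the q8w patient above would have it at the later of Day 337 + 30 = 367 and Day 281 + 56 = 337. The SAP would list 367 days against 336, an excess of 31.

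**The case against.** The strongest reply is that the schedule leaves little room for the error. After discontinuation there is one visit and one contact, and on that path the formula is right to within about a day. A reader might infer from the rules that keep discontinued patients in the study that such patients attend 8-weekly visits for months, and that months of off-drug time will be listed as exposure. The documents do not support that. Table 6-1 schedules no such visits, the asterisk note does not imply them, and safety follow-up can be met by the single contact. Nor do they rule it out: section 6 describes the safety contact as a minimum, and the study has no fixed end.

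A reader might also infer that the SAP contradicts a protocol definition. It does not, because section 9.3 defines none. Where exposure ends after the last dose is a convention, and the 28-day column rests on one choice of it.

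The consequence is small as well. No exposure-adjusted rate or on-treatment flag is planned, all adverse events in both epochs are listed, and dose counts are shown. All of this stands. It limits the size of the point, but it does not make time in study the same thing as exposure, and the formula gives a sensible value for an early stopper only if no later visit takes place.

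**Conclusion.** The definition is wrong as written, and the point is minor. SAP 2.4.1 measures time in study and labels it exposure. For patients dosed up to Visit 199, and for those whose last visit is a discontinuation visit within one dosing interval of the last dose, the excess is about 0 to 1 day. For a patient who stops drug and attends later visits, the formula counts off-drug days. The documents do not say how many such visits there would be, so the excess may be zero; the 113 to 309 days in the table are illustrations under assumed follow-up, not expected values. The examples also assume the first extension dose at Visit 101 and the dose and visit dates shown. The effect is confined to individual listed values for at most 10 patients, and no rate, summary or conclusion depends on it.

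**What to change.** In SAP 2.4.1 and the exposure listing:

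1. List the date of last administration, as already defined in Table 2-1.
2. Define duration of exposure as min(date of last administration + 56 days − 1, date of death, last visit recorded in the clinical database) − date of first extension administration + 1. One fixed 8-week window for all patients leaves nothing open and matches the period after the last injection that protocol sections 3.1.2 and 5.6.1 use for safety follow-up.
3. List the present quantity in its own column, labelled time in study, and state that the safety follow-up contact is not counted as a visit.

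The cost is a revised SAP definition and two listing columns. No new data are needed, since the protocol already requires that "All dosages prescribed and dispensed to the patient and all dose changes during the study must be recorded on the Dosage Administration Record CRF". The downside is that listed exposure becomes shorter for early stoppers who stay in follow-up, and that the window is a convention: in the q4w example with a last visit 8 or more weeks after the last dose, it gives 112 days where a 28-day window would give 84.

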2.4.2 Prior, concomitant and post therapies

Listings will be provided to display prior/concomitant medications or therapies, and medical surgeries and procedures. Specifically, rescue medications will be listed.

Prior medications will be defined as treatments taken and stopped prior to date of first administration of study treatment. Any medication will be defined as a concomitant medication, if it is given at least once on or after date of first administration of study treatment.

Rescue medications will be defined as corticosteroids or NSAIDS provided as concomitant medications.

2.5 Analysis of the primary objective

2.5.1 Primary endpoint

The primary variable is adverse event. Details will be discussed in section 2.8.1.

2.5.2 Statistical hypothesis, model, and method of analysis

Not applicable.

2.5.3 Handling of missing values/censoring/discontinuations

Not applicable.

2.5.4 Supportive analyses

Not applicable.

2.6 Analysis of the key secondary objective

2.6.1 Key secondary endpoint

Not applicable.

2.6.2 Statistical hypothesis, model, and method of analysis

Not applicable.

2.6.3 Handling of missing values/censoring/discontinuations

Not applicable.

2.7 Analysis of secondary efficacy objective(s)

2.7.1 Secondary endpoints

Not applicable.

2.7.2 Statistical hypothesis, model, and method of analysis

Not applicable.

2.7.3 Handling of missing values/censoring/discontinuations

Not applicable.

2.8 Safety analyses

All safety analysis will be based on Safety Set.

2.8.1 Adverse events (AEs)

A listing will be presented to display individual adverse events reported in Epoch 1 and 2.

Also, SAEs will be listed.

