3.1 Study design

Japanese patients are allowed to enter this extension study after completion of Epoch 4 (an open-label treatment epoch) in CACZ885N2301 study. This study consists of two study epochs (Screening epoch and Extension-treatment epoch). This study will be continued until approval in Japan or the discontinuation of the development of the drug in Periodic Fever Syndromes.

In this study, all patients will receive the same dose and regimen as administered at the end of study CACZ885N2301 consisting of 1 or 2 subcutaneous injections every 4 or 8 weeks. Safety will be evaluated every 8 weeks.

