5.6.5 Early study termination by the sponsor

The study can be terminated by Novartis at any time for any reason. This may include reasons related to the benefit risk assessment of participating in the study, practical reasons, or for regulatory or medical reasons (including slow enrolment). Should this be necessary, the patient must be seen as soon as possible and treated as a prematurely withdrawn patient. The investigator may be informed of additional procedures to be followed in order to ensure that adequate consideration is given to the protection of the patient's interests. The investigator will be responsible for informing the Institutional Review Board/Independent Ethics Committee (IRBs/IECs) of the early termination of the trial.

6 Visit schedule and assessments

Table 6-1 lists all of the assessments and indicates with an "x" when the visits are performed.

At a minimum, patients will be contacted for safety evaluations and a follow-up visit or phone call for Serious Adverse Event (SAE) must be performed 30 days following study TD, premature subject withdrawal (PSW) or 8 weeks after last injection of study drug, whichever is later.

Documentation of attempts to contact the patient should be recorded in the patient record.

Table 6-1 Assessment schedule

Epoch	Screening (Epoch 1)	Extension- treatment (Epoch 2)			Safety follow-up
	1#	101#	102, 103....	199 and TD and/or PSW ⁶	
Week (Relative to Baseline of core study)	113	113	121, 129....		
Day	785	785	841, 897....		PSW +30 or 8 weeks after last injection
Informed consent	X				
Demography	X				
Inclusion/Exclusion Criteria	X				
Relevant medical history/ current medical conditions	X				
Prior and concomitant medications (including vaccination status) *	X	X	X	X	
Surgical and medical procedures*	X	X	X	X	
Disease Diagnosis	X				
Disease characteristics	X				
Pregnancy test –urinalysis (for females of child bearing potential) *		S		S	
Physical examination ^{*,7}		S	S	S	
Weight ^{2,3,7}		S	S		
PGA ^{2,4,7}		S	S		
Hematology (local Lab) *		X	X	X	
Blood chemistry (local Lab) *		X	X	X	
CRP (local Lab) ^{2,5,7}		S	S		
Administration of open-label treatment ¹		X	X		
Adverse events*	X	X	X	X	
Local tolerability ^{*,7}		S	S	S	
Screening phase disposition form	X				
Study phase completion form*				X	
Follow-up visit or phone call for SAEs*					S

TD = Study treatment discontinuation; PSW = Premature subject withdrawal

X = assessment to be recorded on clinical data base

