7.1 Adverse events

An adverse event (AE) is any untoward medical occurrence (e.g., any unfavorable and unintended sign [including abnormal laboratory findings], symptom or disease) in a subject or clinical investigation subject *after providing written informed consent* for participation in the study until the end of study visit. Therefore, an AE may or may not be temporally or causally associated with the use of a medicinal (investigational) product.

In addition, all reports of intentional misuse and abuse of the product are also considered an adverse event irrespective if a clinical event has occurred.

The occurrence of adverse events must be sought by non-directive questioning of the patient at each visit during the study. Adverse events also may be detected when they are volunteered by the patient during or between visits or through physical examination findings, laboratory test findings, or other assessments.

Abnormal laboratory values or test results constitute adverse events only if they fulfill at least one of the following criteria:

- they induce clinical signs or symptoms,
- they are considered clinically significant,
- they require therapy.

Clinically significant abnormal laboratory values or test results must be identified through a review of values outside of normal ranges/clinically notable ranges, significant changes from baseline or the previous visit, or values which are considered to be non-typical in patient with underlying disease. Investigators have the responsibility for managing the safety of individual patient and identifying adverse events. Alert ranges for laboratory and other test abnormalities are included in [Appendix 1](#).

Adverse events must be recorded in the Adverse Events CRF under the signs, symptoms or diagnosis associated with them, accompanied by the following information:

- the severity grade
 - a. mild: usually transient in nature and generally not interfering with normal activities
 - b. moderate: sufficiently discomforting to interfere with normal activities
 - c. severe: prevents normal activities
- its relationship to the study treatment
 - Yes
 - No
- its duration (start and end dates) or if the event is ongoing an outcome of not recovered/not resolved must be reported.
- whether it constitutes a serious adverse event (SAE - See [Section 7.2](#) for definition of SAE) and which seriousness criteria have been met.
- action taken regarding [investigational] treatment

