9.4.1 Variable(s)

Primary variable is adverse events.

Adverse events will be coded using the MedDRA dictionary that provides the primary system organ class and preferred term information.

A listing will be presented to display individual adverse events reported.

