2.8.2 Deaths

Deaths will be listed.

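### The primary adverse-event listing stops at Epoch 2, and SAEs first found at the later safety follow-up contact have no assured route into the clinical database

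*SAP*

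**What the plan says.** **Listings.** Adverse events are the only primary variable. Protocol 9.4.1 plans this: "A listing will be presented to display individual adverse events reported". The SAP adds a limit in 2.8.1: "A listing will be presented to display individual adverse events reported in Epoch 1 and 2". The next SAP sentence reads "Also, SAEs will be listed", and SAP 2.8.2 reads "Deaths will be listed"; neither carries an epoch limit or names a data source. SAP section 4, on changes to the protocol-specified analyses, is marked not applicable.

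**Epochs and follow-up.** Protocol 3.1 states: "This study consists of two study epochs (Screening epoch and Extension-treatment epoch"). Table 6-1 gives safety follow-up its own column after Epoch 2, and its footnote 6 sends patients into a safety follow-up period once Visit 199 is done.

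**Data capture.** In Table 6-1 the adverse-event row is coded X (clinical database) from Visit 1 to Visit 199 or the treatment discontinuation (TD) or premature withdrawal (PSW) visit. It is blank at safety follow-up. The only entry in that column is the row "Follow-up visit or phone call for SAEs", coded S, and the legend reads "S = assessment to be recorded on source documentation only".

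**Collection period.** Protocol 7.1 counts adverse events from consent "for participation in the study until the end of study visit", without saying whether that visit is Visit 199 or the follow-up contact. Protocol 7.2.2 sends every SAE to the sponsor on the SAE Report Form within 24 hours.

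**The concern.** The study has one objective, safety and tolerability, and one output for it, a set of listings. The follow-up contact exists to find serious events after treatment has ended. Under the SAP's wording, an SAE first found there is outside the listing of the primary variable, although the protocol's own description of that listing would include it.

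The SAE and death listings could still show the event, but only if their source holds the record. Protocol 8.3 describes a database built from CRF entries, locked and then analysed. Protocol 7.5 mentions a safety database as a separate thing. Neither document says that SAE forms from the follow-up contact feed the listings or are reconciled with the clinical database. The study phase completion form in Table 6-1 is also due only at Visit 199 or the TD/PSW visit, so the table provides no CRF entry for a death found at the contact.

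Sites could therefore differ. One might enter a follow-up SAE on the AE CRF under Protocol 7.1, and another might follow Table 6-1 and keep it in source. With at most 10 patients and no summaries, the listings are the whole reported safety record.

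**Working it through.** This is a question of data scope, so there is no power or sample-size figure to reproduce. The visit calendar and the length of the window can be checked.

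**1. Calendar (Table 6-1).** Day = (week − 1) × 7 + 1.
- Week 113: 112 × 7 + 1 = 785
- Week 121: 120 × 7 + 1 = 841
- Week 129: 128 × 7 + 1 = 897
- Extra q4w visits: 785 + 28 = 813 and 841 + 28 = 869

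All agree with the table and its footnote 1.

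**2. Length of the window.** Inputs:
- The contact is due at the later of 30 days after Visit 199/TD/PSW and 8 weeks (56 days) after the last injection (Protocol 5.6.1).
- Visit 199 is about 8 weeks after the most recent assessment visit (Table 6-1, footnote 6).
- No dose is marked at Visit 199, and adverse events are coded X there.

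Let L be the days from the last injection to the last visit with adverse events coded X. The contact falls on post-dose day max(L + 30, 56), so the window is max(30, 56 − L) days.

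| Case | L | Post-dose days covered by a database visit | Contact on day | Window |
|---|---|---|---|---|
| q8w completer | 56 | 0–56 | max(86, 56) = 86 | 30 days |
| q4w completer, last injection 28 days before Visit 199 | 28 | 0–28 | max(58, 56) = 58 | 30 days |
| TD visit 14 days after last injection | 14 | 0–14 | max(44, 56) = 56 | 42 days |
| TD visit on day of last injection | 0 | none | max(30, 56) = 56 | 56 days |

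The TD rows assume no later visit at which adverse events enter the database.

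**3. Person-time.** For the maximum of 10 patients:
- 10 × 30 / 365.25 = 0.82 patient-years
- 10 × 56 / 365.25 = 1.53 patient-years

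The second figure needs all ten patients to stop on the day of their last injection, so it is an upper bound.

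**4. Chance that it matters.** The documents give no SAE rate. Assuming r = 0.05 to 0.5 SAEs per patient-year, the chance of at least one SAE in the window is 1 − exp(−r × patient-years):
- 0.82 patient-years: 4% to 34%
- 1.53 patient-years: 7% to 54%

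The range follows from the assumed rates and only gives a sense of scale.

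**5. Route of an SAE first found at the contact.**

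| Destination | What the documents provide |
|---|---|
| Sponsor, on the SAE form | Yes (Protocol 7.2.2; 7.1 for events beyond the observation period) |
| AE CRF and clinical database | Not assured: Table 6-1 codes the contact S and has no AE mark; Protocol 7.1 depends on an undefined final visit |
| Primary AE listing | Outside it, on the wording of SAP 2.8.1 |
| SAE and death listings | No epoch limit, but no stated source |

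**The case against.** Four arguments weigh against a stronger reading.

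**The SAE and death listings are unrestricted.** A reader might infer that the SAP excludes follow-up SAEs from all reporting. It does not. SAP 2.8.1 and 2.8.2 promise both listings without an epoch limit, and the contact concerns SAEs. This stands. What it leaves open is whether the source of those listings holds the record.

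**Code S does not bar CRF entry.** A reader might infer that follow-up SAEs are kept out of the clinical database. Physical examination is also coded S, yet Protocol 6.5.1 sends findings that qualify as adverse events to the AE section of the CRF. An S on the contact may mean only that the call itself is documented in source. This also stands, so exclusion is not established. But the AE row is blank at follow-up, and nothing equivalent to 6.5.1 covers the contact.

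**Two epochs may mean the whole study.** No third epoch is defined, and the SAP declares no departure from the protocol, so the limit may be loose wording. That is possible. However, footnote 6 and the separate column put follow-up after Visit 199, so the sentence needs rewording on either reading.

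**The window is limited.** A reader might infer that all SAEs in the weeks after the last dose are lost. For completers, the first 4 to 8 weeks after the last dose are covered at Visit 199. The 56-day case is a corner case: Protocol 5.6.2 keeps patients who stop treatment in the study, and 6.5 keeps their safety assessments mandatory, so later database visits may shorten it.

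It is also tempting to say that one missing SAE in 10 patients moves the incidence by 10 percentage points. That does not hold. SAP 2.1 plans no statistical summary, and patient incidence would not change if that patient already had an SAE.

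**Conclusion.** The point holds as a gap in scope and data flow, not as a demonstrated loss of SAEs. SAP 2.8.1 is narrower than Protocol 9.4.1 without a declaration in SAP section 4, and on its wording an SAE first found at the follow-up contact is outside the primary listing. Expedited reporting to the sponsor is intact. Appearance in the SAE and death listings is permitted by the SAP but not secured by any stated data route.

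The size is that of steps 2 and 3 of the working: about 30 days per completer, with 56 days as the individual maximum. This rests on three things: reading the separate follow-up column as outside Epoch 2, taking Visit 199 or the TD visit as the last visit with adverse events entered in the database, and last-injection timings as tabulated. The correction should be made because the listings are the study's only safety output and the change is small.

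**What to change.** 1. **Protocol Table 6-1:** mark SAEs found at the safety follow-up contact for entry on the AE CRF (X). The call itself can stay in source.
2. **Protocol 7.1:** define the final visit that closes adverse-event collection, and tie it to the safety follow-up contact for SAEs.
3. **SAP 2.8.1 and 2.8.2:** state that the AE, SAE and death listings include all events through that contact, that they draw on the clinical database, and that it is reconciled with the SAE forms before lock. SAP 2.8.1 then no longer falls short of Protocol 9.4.1.

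A column for phase of onset is optional, since SAP Table 2-1 already defines Extension Study Day.

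The cost is one table mark, a few sentences and a few extra CRF entries. No visit, contact or procedure is added.
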